- (3) Imaging examination: routine examination of X-ray, CT plain scan without lumbar spine and intraspinal tumors;
 - (4) No history of lumbar back surgery.

References involved:

- [1] O Airaksinen, J I Brox, C Cedraschi, et al. on behalf of the COST B13 Working Group on Guidelines for Chronic Low Back Pain. European guidelines for the management of chronic no nspecificlow back pain[J]. Eur Spine J, 2006, 15 (Suppl. 2):S192-S300.
- [2] TROYER M R.Differential Diagnosis of Endometriosis in a Young Adult Woman With Nonspe cific Low Back Pain[J]. Phys Ther, 2007, 87(6):801-810.

2. Inclusion criteria:

① Compliance with the diagnostic criteria for low back pain and the syndrome differentiation criteria

for cold and wet lumbar muscle strain

- 2) Sex is not limited, and the age is controlled between 25 years and 70 years old
- 3 Not nearly 2 weeks ago
- 4 The disease course was controlled within 8 years
- ⑤ Informed consent and willing to cooperate with the whole treatment
- (6) They agreed to record the scale score and volunteered to participate in this trial
- 7 Patients reserve at least one contact information for easy follow-up
- ® To reduce the shedding rate, the inpatients should be preferentially included
- Patients with lumbar disc herniation, lumbar disc bulging, sacral canal cyst, nerve root compression,
 and lumbar bone hyperplasia were included

Those who meet the above 9 items can only be included in this study.

Exclusion criteria:

- ① Patients did not meet the inclusion criteria Patients who did not meet the inclusion criteria for the diagnosis of this topic
- 2 The patient is in pregnancy or lactation
- 3 Patients are allergic to moxibustion smoke, and it is difficult to accept moxibustion treatment
- ④ The patient had diseases of the blood and immune system
- (5) The patient had cardiac, hepatic, and renal insufficiency
- ⑥ The patient suffered from mental illness and failed to cooperate with moxibustion
- ① Low back pain caused by lumbar spine and spinal canal tumors, lumbar scoliosis, bladder diseases, and gynecological diseases
- Patients with a previous history of lumbar spine surgery

blind method:

RCT randomization (difficult to implement blind method, intuitive difference between robot moxibustion and artificial moxibustion)

(Because of this experiment, total blindness cannot be achieved. Unlike drugs that can mask it,

In this experiment, the patients and the doctors saw the real "robot" or "artificial", which could not be done too much blind method.

 $Therefore, \ to \ maximize \ blinding, \ staff \ are \ advised \ to \ communicate \ with \ the \ patient \ in \ the \ following \ manner:$

- 1. Multicenter trials, human and robot groups respectively in independent experimental centers
- 2. Ensure that the "artificial group" does not know the existence of moxibustion robot, so as not to ask patients to use the robot or artificial moxibustion psychological bias and other situations, affect the treatment effect.
- 3. In terms of "robot group", patients can know that moxibustion can be operated by hand with common sense, and the robot is a new scientific research product. In order to ensure that the patient has no bias against the robot, so as to avoid psychological factors affecting the effect.

So to inform the patient that the ingredients in the robot is the same, but the robot has a little advantage in tobacco control and temperature control.)

Group method: random number table method

160 patients were numbered in the order of enrollment (come, come), Using random numbers tables, 160 patients were randomly and equally divided into two groups (chart below)

	机器人组(15)					人工组(15)			
4	14	24	6	8	12	18	23	26	17
30	10	19	1	20	29	2	3	7	13
25	5	16	27	9	11	15	21	28	22

机器人组(10)					人工组(10)				
8	20	3	12	2	11	18	14	13	4
16	6	15	10	19	5	7	1	17	9

机器人组(40)				人工组(40)					
35	65	8	73	26	22	7	57	36	66
31	24	13	54	78	14	46	49	17	64
19	58	38	15	5	55	56	20	4	27
79	12	1	52	33	45	3	63	41	76
42	68	67	50	2	16	47	11	51	20
6	44	10	29	34	39	70	69	32	80
62	23	60	48	75	40	25	53	71	72
43	61	30	18	37	28	77	59	9	74

Intervention mode:

Artificial moxibustion group vs. intelligent thunder-fire moxibustion group

1. Selection of points:

Taking taking: referring to the planning textbook "Treatment of Acupuncture and Moxibustion" of national Universities of Traditional Chinese Medicine edited by Gao Shutong, taking nephroshu, large intestine, YaoYangguan and a point.

Positioning: Select according to relevant provisions of National Standard for Positioning of Acupuncture and Acupuncture (formulated by national GB1234-90 standard).

Kidney yu: in the waist, when the second lumbar spinous process, the side open 1.5 inches. Two bilateral holes were selected each time.

Large intestine yu: in the waist, when the fourth lumbar spinous process, the side open 1.5 inches. Two bilateral holes were selected each time.

Waist Yang: in the waist, when the posterior midline, the fourth lumbar spinprocess in the depression.

2. Course of treatment:

10 treatments for 40min.

(Each patient does it 5 times a week, and patients are usually treated for 2-3 weeks)

3. The operation mode of the moxibustion robot

(Artificial moxibustion, acupoints, technique, duration, all the same)

Enter the setting page of intelligent thunder and fire moxibustion "free moxibustion", and use the rocker to control the six degrees of freedom robotic arm in the lumbar back of patients —— kidney yu, large intestine yu, waist yangguan, a right point.

After positioning, ignite and install the lightning fire moxibustion moxa strip, and set the moxibustion operation —— on the operation page

Kidney Yu BL23, left and right 2 points, linear reciprocating moxibustion (10min) intestinal BL25, left and right 2 points, linear reciprocating moxibustion (10min) DU3, single point, rotary moxibustion (10min)

A is point Pain point, if unilateral pain, sparrow peck moxibustion (10min), if bilateral pain, reciprocating moxibustion (10min)

A total of 40min was used

The operation method of reciprocating moxibustion is: plane straight reciprocating moxibustion, the mechanical arm holds the ignited thunder fire moxibustion line above the above two acupoints;

The operation method of rotary moxibustion is as follows: plane rotary moxibustion, the mechanical arm holds the ignited lightning fire moxibustion bar for parallel reciprocrotary moxibustion above the above acupoints, with a rotary radius of 4cm;

The operation method of sparrow pecking moxibustion is: the mechanical arm holds the selected point, and uses the moxibustion, and the lifting range is 5cm, giving strong warm stimulation; the moxibustion distance is manually adjusted according to the tolerance temperature of the patient.

Note: Visit the ward at any time, observe the skin condition and the heat resistance of the patient, and take the patient comfort.

If there is discomfort, immediately stop the treatment, symptomatic treatment

4. Follow-up:

Each patient is registered with their mobile phone number,

VAS score, JOA score, RMDQ score, and SF-36 score were observed and recorded before, after 5 times, after 10 times of treatment and 2 weeks after completion of treatment (follow-up).

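### Keeping manual-arm patients unaware of the robot cannot be combined with informed consent from every patient before individual randomisation

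*Protocol*

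**What the plan says.** Protocol, Inclusion criteria. Item 5 reads "Informed consent and willing to cooperate with the whole treatment" and item 6 reads "They agreed to record the scale score and volunteered to participate in this trial". The list closes with "Those who meet the above 9 items can only be included in this study", so both items bind the manual arm as well as the robot arm.

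Protocol, blind method. The section concedes that patients and doctors can see which treatment is given. It then advises staff how to talk to patients, in three items:

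- Item 1: "Multicenter trials, human and robot groups respectively in independent experimental centers".
- Item 2: "Ensure that the 'artificial group' does not know the existence of moxibustion robot". The stated purpose is to stop patients' preferences from influencing the treatment effect.
- Item 3, for the robot group: "patients can know that moxibustion can be operated by hand with common sense, and the robot is a new scientific research product". These patients are also to be told that the material is the same but that the robot is slightly better at controlling smoke and temperature.

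Protocol, Group method. "160 patients were numbered in the order of enrollment", and a random number table then splits them equally. The printed tables hold 15 robot and 15 manual numbers, 10 and 10, and 40 and 40.

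The attached ethics opinion states that the right of informed consent is protected. The protocol describes no waiver, partial disclosure or consent after randomisation.

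**The concern.** Before allocation, a patient may go to either arm. Consent to the comparison at that point means being told of the robot, and half of those told will then receive manual moxibustion. Item 2 asks staff to prevent exactly that. The protocol does not say when consent is taken relative to allocation, so each site has to find its own way round the conflict.

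The statistical stake is comparability of the arms. If one arm learns something the other does not, refusal and withdrawal can differ between arms for reasons tied to the treatment. If one arm is also told that its treatment has an advantage, expectation can differ. VAS, JOA, RMDQ and SF-36 are all labelled subjective in the outcome table, so expectation can act directly on the scores. Lumbar range of motion, the Schober test and the serum factors are less exposed to expectation, but they are just as exposed to selective loss of patients.

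**Working it through.** The protocol gives no figure on this point to reproduce, so the check sets its instructions against each other.

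**Can the instructions hold together?** Take three conditions:

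- A: every patient consents, before allocation, to a trial comparing robot and manual moxibustion (inclusion items 5 and 6).
- B: individuals are allocated 1:1 in order of enrolment (Group method).
- C: no manual-arm patient knows that the robot exists (blinding item 2).

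Under A, every patient knows of the robot before allocation. Under B, half of these patients, 80 of 160, become the manual arm. They therefore know of the robot, and C fails. To keep C, a site has two routes:

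1. Tell nobody about the robot before allocation. Information is then equal up to allocation, but no patient has agreed to the comparison actually made, and robot patients learn of the robot afterwards.
2. Let the information follow the arm. Consent is then completed once the arm is known, and manual patients still do not learn what they are compared with. The allocation numbers are printed in the protocol, so staff who hold it could see the arm in advance. No text says that they look it up.

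**Do separate centres (item 1) resolve it?** The hospital quotas are 80, 30, 30 and 20, which add up to 160. The printed lists have 40 + 40 = 80, 15 + 15 = 30 and 10 + 10 = 20 numbers. The list sizes match the quotas and each list contains both arms, so the tables describe both arms within a hospital, contrary to item 1. If the centres did hold one arm each, the arm would be fixed by centre before consent, and manual patients would still enter a robot trial without knowing of the robot. The conflict remains.

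**Can the bias be sized?** Only with assumptions. Let p = 0.7619, the effective rate in the sample size attachment. Let f be the fraction of robot-allocated patients who refuse and are left out of the analysis, and r the response rate they would have had. The rate among those retained is (p − f·r)/(1 − f), so the shift is f(p − r)/(1 − f). The values of f and r below are assumptions; r = 0 and r = 1 are the extremes.

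| f | r | Rate among retained | Shift (points) |
|---|---|---|---|
| 0.10 | 0 | 0.7619/0.90 = 0.847 | +8.5 |
| 0.10 | 0.50 | 0.7119/0.90 = 0.791 | +2.9 |
| 0.10 | 1 | 0.6619/0.90 = 0.735 | −2.6 |
| 0.20 | 0 | 0.7619/0.80 = 0.952 | +19.0 |
| 0.20 | 0.40 | 0.6819/0.80 = 0.852 | +9.0 |
| 0.20 | 1 | 0.5619/0.80 = 0.702 | −6.0 |

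The shift is positive when r is below p, zero when r equals p, and negative when r is above p. The documents give neither f nor r, so they fix neither sign nor size.

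**The case against.** The strongest case on the other side has five parts.

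- The blinding items are advice on communication, not entry rules. This is correct, and the conflict should be described as one between advice and an entry criterion. Item 2 is still worded as something to ensure, and staff who follow it cannot also obtain consent to the comparison.
- A reader might infer that manual-arm consent is invalid. The documents do not support that. The consent pages are not in the text at hand, inclusion item 5 sets no content for the consent, and the ethics opinion was given on a submission that names both the robot and the manual comparison. What the committee accepted as disclosure cannot be seen.
- A reader might infer that only robot-arm patients can refuse or withdraw, so that self-selection is inevitable. That does not follow. Manual patients can refuse or withdraw too, and the 20% shedding allowance is not split by arm. Under route 1, information is equal up to allocation, and selection bias from later refusal arises if those refusers are dropped. The analysis set may be defined in a statistical analysis plan that is not shown.
- A reader might take +2.9 or +9.0 points as the expected bias and set it against the 10 to 15 point equivalence limit. Both values are computed correctly but rest on assumed inputs chosen in one direction.
- Item 2 has a legitimate aim. Manual patients who know of a robot may be disappointed, and that could affect subjective scores. This stands as a real cost of the fix.

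**Conclusion.** The point stands as a conflict within the protocol. Informed consent to the trial from every patient, individual allocation from lists holding both arms, and a manual arm unaware of the robot cannot all be achieved. Items 2 and 3 together lead to information that differs by arm. This creates a risk, not a demonstrated bias, of differential refusal or withdrawal and of differential expectation on the four subjective scales. It concerns all 80 planned manual-arm patients, and the arm-specific message concerns the 80 robot-arm patients.

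The conclusion depends only on the protocol's own instructions and on no numerical assumption. It does not extend to invalid consent, to inevitable self-selection or to a stated shift in the response rate. Analysing refusers as allocated limits the selection problem, but it cannot remove a difference in expectation, so the text should be corrected at the design stage.

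**What to change.** - Delete blinding item 2, and delete from item 3 the message about the robot's advantage.
- Reconcile blinding item 1 with the allocation tables, so that the protocol says one thing about whether each hospital treats one arm or both.
- Add to inclusion item 5 that every patient signs one common consent form, describing both treatments in the same neutral words, before an allocation number is assigned.
- State that anyone who refuses or withdraws after allocation stays in the allocated group for analysis.

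This needs a protocol and consent-form amendment with ethics review, but no extra patients. The ethics page gives a study period of 2022.01.01 to 2023.12.31 and the protocol is dated 2022.12.15, so some patients may already have been enrolled. If so, record what each was told and when.

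The downside is that all manual-arm patients will know that a robot arm exists. Some may be disappointed, which could affect their subjective scores. No treatment masking is lost, because the protocol already accepts that patients see their own treatment.

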Serum Material 1. Collect Before enrollment. inflammatory Serum separation tubes (hospital-provided), content Through all treatments response 4 mL of venous blood. after factor: Before and after treatment, 2 times in total 10 treatments, an average Venvenous blood 2. Place of 2 week. Whole blood specimens collected in serum separation tubes 4 mL, isolated serum, were left at room temperature for 2 hours or 4 oC Detection by overnight, the ELISA 广告 method 1. Serum tumor necrosis factor (TNF- α), 2. Interleukin IL 1β, . Centrization respectively Then centrifuged at 1,000 g for 20 min and the supernatant 3, the was removed, interleukin IL 6, and the 4. Serum thromboxane B2 (TXB 2) level. 4. Freeze Place the supernatant in the frozen storage tube (the last received test tube), which can be inserted in the plastic box hole for easy storage. Refrigerator preservation.-20 $^{\circ}$ C (save for one month) or-80℃ to avoid repeated freezing and thawing. Post inspection After the collection, it will be packaged and mailed to the testing center for testing Foam case shell, with dry ice inside,

Number of tasks per hospital:

1. 80 people in Shanxi Acupuncture and Moxibustion Hospital

[name], [name], [name]

2. 30 people from Xinghualing District Hospital of Traditional Chinese Medicine

The Hospital of Traditional Chinese Medicine, [name]

3. 30 people from Yongji City Hospital of Traditional Chinese Medicine

Yongji City Hospital of Traditional Chinese Medicine, [name], [name]

4. Lingqiu County Hospital of Traditional Chinese Medicine, 20 people

[name], [name] Hospital of Traditional Chinese Medicine, Lingqiu County, Datong City, Shanxi Province [name]

Hospitals should recruit as soon as possible, such as the recruitment of patients due to the epidemic and other factors, timely communication and overall arrangements.

Attached: Sample size calculation

1. According to the review paper, the effective rate of artificial moxibustion is about 76.19%

(Ref.: Effect of thunder-fire moxibustion combined with oblique round blade on electromyography and serum MMP 13 and PGE 2 levels in patients with lumbar intervertebral disc herniation)

Since the robot is a new product with unknown efficiency, it is assumed that it is equivalent to artificial efficiency

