- 2. Statistically speaking, the response efficiency difference between the two groups is $10^{\sim}15\%$, and the two groups are considered equivalent
- 3. Use the pass2011 software

[figure not shown]
Test type: Equivalent test

Calculation method: rate difference method

Efficiency difference value \triangle : 15%, Calculation result: 62 persons / group

The specific steps are described as follows:

Set, efficiency difference 15%. To 62 people / group, (the larger the value, the smaller the sample size)

Ethical approval document of Biomedical Research Ethics Committee of Shanxi Acupuncture Research Institute 伦审科 2022 第 (020) 号

project name	Clinical Study on the Treatment of Low Back Pain with Intelligent Moxibustion Robot: A Randomized Clinical Control Experiment						
Project category	foundation C	clinical	O medicina	1 🗆			
project leader	[name]	Study start and end time	2022.01.01 2023.1	2.31			
[contact]						
Project source	1.Shanxi Provincial Health Commission major scientific research project 2.Science and Technology Innovation Team of Shanxi University of Traditional Chinese Medicine						
Application unit	Shanxi Provincial Acupuncture and Moxibustion Hospital						
Submit review ma	Submit review materials: ○Application for project ○ research paper □other						
Decearch main content.							

A "thunder fire moxibustion intelligent robot" was developed jointly with Central North University to compare the traditional artificial moxibustion group by applying the moxibustion robot prototype to the clinic. Under the condition that the duration, acupoints and techniques of moxibustion are the same, 80 patients with low back pain with similar conditions were treated, and the relief of low back pain symptoms were observed after 10 times of moxibustion, so as to clarify the moxibustion efficiency, efficacy and safety of the moxibustion robot, and to provide a new direction for the research and development of intelligent moxibustion products.

Ethics Committee opinion: Upon review, the experimental design and protocol of the study fully considered the principles of safety and fairness, and protected the experimental subjects' right of informed consent. There is no conflict of exami ne interest in the study content and findings. bear fruit ORetrial after modification O disagree Ethics Committee official seal: Date :

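### Staff are advised to tell only robot-arm patients that the robot has an advantage, which risks expectation bias in the subjective scales of an open equivalence trial

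*Protocol*

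**What the plan says.** All references are to the Protocol.

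- **Blind method, opening.** Blinding is described as not really achievable: "In this experiment, the patients and the doctors saw the real" treatment, robot or manual. Three measures follow, advising staff how to communicate with patients so that blinding is as good as it can be.
- **Blind method, measure 2.** The manual group is to be handled so that it "does not know the existence of moxibustion robot".
- **Blind method, measure 3.** For the robot group, the aim is that patients hold no bias against the robot, "so as to avoid psychological factors affecting the effect". Patients are therefore to be informed that the ingredients are the same, but that "the robot has a little advantage in tobacco control and temperature control". Here tobacco evidently stands for moxa smoke.
- **Intervention mode, 4. Follow-up.** "VAS score, JOA score, RMDQ score, and SF-36 score were observed and recorded before" treatment, after 5 and 10 treatments, and 2 weeks after completion. The Outcome indicators table labels all four scales as subjective.
- **Attached: Sample size calculation.** "Since the robot is a new product with unknown efficiency", its effective rate is set equal to the manual rate of 76.19%. The calculation is headed "Test type: Equivalent test", with a difference of 15%.

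**The concern.** Measure 3 sets out to remove a possible prejudice against the robot. Neutral wording would serve that aim. The script goes further and tells patients that the device they are about to receive is somewhat better in two respects. Measure 2 rules out saying the same to the manual arm, and the protocol contains no counterpart message for it.

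The patients who hear this know what they are receiving and then score their own pain, function and quality of life three more times. A favourable remark made to one arm may shift those scores. Range of motion, the Schober test and the serum markers are less exposed.

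The equivalence objective sharpens the point. Equivalence is concluded when the observed difference is small, so a lift in the robot arm can hide a true robot deficit. Enrolling more patients does not remove such a shift.

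**Working it through.** **Reading the text.** The concern rests on no figure in the plan, so there is none to reproduce. Four statements carry it:

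1. The message is favourable (measure 3).
2. It can reach only the robot arm (measure 2).
3. Patients know their treatment (blind method, opening).
4. Four outcome scales are labelled subjective (Outcome indicators).

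Together these show a one-sided influence on subjective scores, created by a measure meant to prevent such influences.

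**How much it could matter (illustration).**

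Inputs from the protocol: manual effective rate pm = 0.7619, margin 0.15, and 62 per group (calculated) or 80 per group (planned).

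Assumptions not in the readable text:
- two one-sided tests at 5% (z = 1.645), with 2.5% (z = 1.960) as an alternative;
- a lift b in the robot arm's observed effective rate of 0, 2, 5 or 10 points;
- a shift in the scales carries over to the effective rate, which the protocol does not define.

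Formulas, with pr the observed robot rate:

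- SE = √{[pm(1 − pm) + pr(1 − pr)]/n}, and d = pr − pm
- P(equivalence) = max{0, Φ[(0.15 − z·SE − d)/SE] − Φ[(−0.15 + z·SE − d)/SE]}

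*Case A: the robot is truly 15 points worse*, so pr = 0.6119 + b and any declaration of equivalence is wrong.

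Worked for n = 80, z = 1.645:

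- b = 0: SE = √[(0.1814 + 0.2375)/80] = 0.0724 and d = −0.15, so P = Φ(2.501) − Φ(1.645) = 0.044.
- b = 0.05: pr = 0.6619, SE = √[(0.1814 + 0.2238)/80] = 0.0712 and d = −0.10, so P = Φ(1.868) − Φ(0.942) = 0.142.

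| Lift | 62/group, 5% tests | 80/group, 5% tests | 80/group, 2.5% tests |
|---|---|---|---|
| 0 | 2.8% | 4.4% | 1.1% |
| 2 points | 4.3% | 7.4% | 2.0% |
| 5 points | 7.8% | 14.2% | 4.4% |
| 10 points | 16.5% | 30.9% | 12.2% |

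Exact binomial enumeration with Wald bounds agrees closely for the 5% tests: 2.6%, 4.3%, 8.1% and 17.7% at 62 per group, and 4.5%, 7.5%, 14.3% and 31.2% at 80. With 2.5% tests at 62 per group, the normal approximation gives zero and exact enumeration at most 1.9%.

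*Case B: the arms are truly equal*, as the sample size section assumes, so pr = 0.7619 + b. Probability of correctly showing equivalence, 5% tests:

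| Lift | 62/group | 80/group |
|---|---|---|
| 0 | 24.8% | 44.0% |
| 2 points | 26.2% | 44.4% |
| 5 points | 24.9% | 38.8% |
| 10 points | 15.1% | 19.6% |

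The same lift can therefore support a false claim of equivalence or defeat a true one, depending on the real difference.

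**The case against.** The strongest reply is that the message is mild and has a purpose. It begins by saying the ingredients are the same, calls the advantage small, and speaks of smoke and temperature control, not of pain or function. On that reading it does not contradict the statement that the robot's efficiency is unknown. If patients distrust a new machine, the remark may bring them nearer to neutral. Staff are only advised to use it. Case A above takes the least favourable setting: a true deficit exactly at the margin, a purely positive lift and full carry-over to the effective rate. Deleting the sentence also leaves a larger asymmetry, since one arm sees a novel robot and the other does not know it exists.

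Much of this stands. The size and net direction of any effect are unknown, the illustration depends on its assumptions, and Case B shows that small lifts matter little when the arms are equal. The unknown-efficiency statement shows only that the plan starts without a presumption in the robot's favour.

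The objection does not rescue the sentence. Moxibustion is a heat treatment whose distance is adjusted to the patient's temperature tolerance, so better temperature control is easily heard as better treatment. The protocol shows neither that distrust exists nor that this remark would just offset it. Seeing the treatment is unavoidable here; a scripted claim of advantage is not.

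**Conclusion.** The concern holds. The protocol scripts a favourable statement that can reach only the robot arm of an open trial with four subjective scales, and so works against its own aim. This is an avoidable risk of bias, not a demonstrated bias.

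Its size cannot be settled from the document. Under the stated assumptions, at 80 per group with 5% tests and a true 15-point deficit, a 2- to 10-point lift raises false equivalence from 4.4% to between 7.4% and 30.9%. At 62 per group the rise is from 2.8% to between 4.3% and 16.5%. With 2.5% tests the risk is smaller, and at 62 per group it stays under 2%. The conclusion does not depend on these figures. The statement that the manual arm gets no counterpart message rests on the protocol text at hand, from which consent pages were removed. The change should be made; confidence in its practical importance is medium.

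**What to change.** Delete the advantage claim from measure 3 and give both arms the same neutral statement, for example: *You will receive moxibustion with the materials, acupoints, technique and duration fixed in the protocol; how well it works is what the study measures.* The robot arm is told in addition only that a robot delivers the treatment, with no suggestion that this is better. Measure 2 can stay.

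The cost is one sentence of the staff script. The small downside is that any distrust of the robot is no longer actively countered. The change does not remove the asymmetry that comes from seeing the robot.

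A further option is one common neutral script for all patients before the assignment is revealed. This costs more: manual-arm patients would learn of the robot and might ask for it or be disappointed. That would act on the same scales and is what measure 2 tries to prevent.
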